**Up and Down: Use of Dynamic Partial Body Weight Support
Play Environment to Encourage Upright Mobility and
Exploration in Infants with Down Syndrome (DS)**

NCT number:

Date: 1/06/2022

Statistical Design and Power

Data Analysis:

All statistical analyses will be conducted using SPSS (version 27.0 IBM, Armonk, NY). Descriptive participant characteristics (e.g., age, sex, race/ethnicity, DS type) will be summarized as categorical variables. The dependent variables for this study are exploratory behavior activity counts, exploratory behavior coding counts, GMFM sections D and E raw scores, and DMQ-18 raw scores. Descriptive statistics will be reported for each variable. To test whether there is a difference in conditions for each dependent variable, paired t-tests will be performed comparing the control post-tests to the intervention post-tests. Prior to statistical analysis, we will test the data for normality. If the data is not normally distributed, differences will be determined using the Wilcoxon Rank Sum test. Alpha will be set at 0.05.

Movement counts will be analysed using the Actilife 6 software (ActiGraph, Pensacola, FL). Each intervention session will be video recorded, and exploratory activity will also be coded from the recordings. Coding will be conducted using a momentary time sampling strategy from the videos of the first session of week 2 and week 6 (first exposure to the play environment in each condition) and the last session of week 4 and week 8 (last exposure to the play environment in each condition). Coding metrics will include physical activity, classified according to the Observational System for Recording Physical Activity in Children- Preschool version, social interactions, classified according to the Code for Active Student Participation and Engagement- Revised (CASPER-III), and object-related actions, classified by whether a child is touching, holding, or using a portable object with their hands using a categorical yes/no binary²⁸. Inter- and intra-rater reliability of at least 90% agreement will be established for each exploratory behavior on 10% of the video recordings using the ratio of [agreements/ (agreements + disagreements) X100] to establish a percentage of agreement.

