Participants will include children of all genders, with Down Syndrome (any form) diagnosis, under 36 months of age, able to sit independently and one parent or legal guardian of all genders ages 18 and above. Inclusion criteria for the study: 1) The child will have a medical diagnosis of DS (any form); 2) be under 36 months old; 3) able to sit independently; 4) one parent must be able to read proficiently enough in English to complete a written assessment. Children will be excluded from the study if: 1) they can walk independently; 2) have uncontrolled seizures; 3) have known medical precautions that would prohibit them from wearing a harness; 4) have other developmental disability diagnoses. Participants will be recruited by the research team via social media postings, emails to known rehabilitation professionals in the Seattle region, and via fliers hung-up and passed out at local healthcare clinics and hospitals. The research team will also send emails to past research participants who had shared their email address and had agreed to be contacted for future studies. Potential participants will self-elect to call or email the research team to hear more about the study to determine whether or not they are interested in participating. Interested potential participants would then be screened for eligibility by a member of the research team.

We will conduct our work in this pilot study using a randomized, crossover design with children serving as their own controls. Study activities for each child will take place over 9 weeks in the PI's research lab on UW campus (CHDD buildings). After successful recruitment, children baseline assessment will be conducted during week one. On the first visit, parents will be asked to review and sign informed consent documentation to participate and baseline assessments will be completed. Then randomization assignment into 2 groups for intervention either play sessions using the PBWS (harness) or control play group (no harness, 3 sessions per week) for 3 weeks (weeks 2-4 of the study and weeks 6-8), with a washout and reassessment period during week 5 prior to crossover. A final reassessment session will be done during week 9.

Figure 1. (Left) Portable PUMA system for Partial Body Weight Support in an Enriched Environment; **(Right)** Close up photo of the harness attachment and portable frame components.

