Equipment: Each child will be introduced to an 81 square foot play environment with dynamic enrichment (PEDE). The PEDE will consist of a **Portable Mobility Aid for Children (PUMA) system and a PBWS harness** that offers 1, 2, 4, or 8 lb counterweighting (Enliten, Newark, DE, USA, images of the system at <https://www.enlitenllc.com/puma.html>) as well as toys and toy placement that facilitates upright exploration. A **standardized set of toys and equipment** will be used at each site for consistency. The **PEDE** will be set up over bi-colored 12" x 12" interlocking floor tiles to provide a firm yet padded play surface and also allow for straightforward measurement of movement trajectories across the play space. Standardized toys will include but not be limited to a set of four nesting benches, a crawl-in play cube, a manipulative activity cube that can be accessed in seated or standing positions, cause and effect toys, and sensory play items such as a Montessori Busy Board. (See Appendix B for photos of proposed standardized toys).

In the control condition, children will be placed in the PEDE but not attached to the PUMA or harness. In the experimental condition, children will be placed in the harness and attached to the PUMA, which acts as a partial body weight support. In both conditions, the children will be placed in sitting initially, and though the researchers will encourage the children to stand through placement of toys and verbal/visual cues, position changes will not be imposed by researchers or caregivers. While in the PEDE, children will play for up to 30 minutes within a 60-minute appointment. Children will be given breaks as needed based on the following criteria: the child cannot be redirected, distracted, or calmed by parent/researcher for more than 1 min with repeated attempts to engage/distract; the child falls asleep; there is a safety concern or harness slippage; or the parent requests a break for their child. Once a child reaches 30 minutes of exposure to the PEDE or the 60-minute appointment time ends, the child's intervention session will end for the day. The amount of time in the harness and PUMA system will be documented at each study visit.

Dependent Measures:

Aim 1: Explore the effects of a harness-based intervention on exploratory behavior among infants with DS

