Exploratory behavior expressed as activity counts during all intervention and control play sessions will be measured using **wrist and ankle mounted accelerometers (Actigraph GT3X+)**. These passive sensors will be placed on the child's right-side wrist and ankle and covered with wrist bands. The sensors will be

set to capture data in 1 second epochs. Each intervention session will be video recorded, and exploratory activity will also be coded from the recordings. Coding will be conducted using a momentary time sampling strategy from the videos of the first session of week 2 and week 6 (first exposure to the play environment in each condition) and the last session of week 4 and week 8 (last exposure to the play environment in each condition). Coding metrics will include physical activity, classified according to the Observational System for Recording Physical Activity in Children- Preschool version, social interactions, classified according to the **Code for Active Student Participation and Engagement-Revised (CASPER-III)**, and object-related actions, classified by whether a child is touching, holding, or using a portable object with their hands using a categorical yes/no binary. (See Appendix A for a detailed description of the behavioral coding scheme). Inter- and intra-rater reliability of at least 90% agreement will be established for each exploratory behavior on 10% of the video recordings using the ratio of [agreements/ (agreements + disagreements) X100] to establish a percentage of agreement.

Aim 2: Explore the effects of a harness-based intervention on gross motor skill acquisition among infants with DS

Standardized study assessments will occur at the initial study session, during week 5 (midpoint), and during week 9 (post-test). The **Gross Motor Function Measure-88 (GMFM)** will be used to assess gross motor development. Specifically, we will use sections D (Standing), and E, (Walking, Running & Jumping). The GMFM-88 is a reliable measurement tool and is valid for children with Down syndrome. The GMFM-88 will be administered by the site investigator but will be scored by a single, blinded, trained assessor via video recording.

Aim 3: Explore the effects of a harness-based intervention on parent-reported mastery motivation among infants with DS

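### The crossover is analysed without a period term, which costs precision and, if the two orders end up unequal, shifts the estimate

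*SAP*

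**What the plan says.** The protocol (Research Design and Methods) describes a randomised crossover in which each child receives both conditions. Play blocks run in weeks 2-4 and 6-8, with washout and reassessment in week 5 and a final reassessment in week 9.

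The SAP (Data Analysis) names one between-condition comparison per outcome: "paired t-tests will be performed comparing the control post-tests to the intervention post-tests". Its fallback reads: "If the data is not normally distributed, differences will be determined using the Wilcoxon Rank Sum test". Neither document mentions a period effect, a sequence effect or any analysis by order.

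Measurement times differ systematically by period:

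- GMFM (Protocol, Aim 2) is assessed at the initial session, then "during week 5 (midpoint), and during week 9 (post-test").
- Accelerometry (Protocol, Aim 1) covers "activity counts during all intervention and control play sessions".
- Video coding (Protocol, Aim 1) uses "the first session of week 2 and week 6 (first exposure to the play environment in each condition"), and the last sessions of weeks 4 and 8.
- For DMQ-18 (Protocol, Aim 3) no timing is given. It presumably follows GMFM.

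The play space is common to both conditions (Protocol, Equipment): "In the control condition, children will be placed in the PEDE but not attached to the PUMA or harness".

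**The concern.** In a two-period crossover, half the information on condition comes from children measured under harness first and half from children measured under control first. Anything that changes between periods for every child enters the intervention-minus-control difference with opposite signs in the two orders. A paired test that ignores order treats this as random variation between children. If the orders are unequal in size, the two signs no longer cancel.

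The documents give reason to expect such a change for two of the three aims. Aim 2 is about acquiring gross motor skill, in children under 36 months who cannot yet walk, with post-tests four weeks apart. For Aim 1, every child has already spent a full block in the same play environment by week 6, whichever order was assigned. The documents give no comparable reason for DMQ-18.

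Using each child as its own control is meant to give a small pilot its precision. The planned test can give part of that back.

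**Working it through.** **Inputs from the documents.** Two conditions, two periods, randomised order, and alpha 0.05 (taken as two-sided). The play block is described as "control play group (no harness, 3 sessions per week) for 3 weeks (weeks 2-4 of the study and weeks 6-8"), and "While in the PEDE, children will play for up to 30 minutes within a 60-minute appointment". If three sessions a week applies to both conditions, prior exposure by week 6 is 3 × 3 = 9 sessions, up to 9 × 30 = 270 minutes (4.5 hours).

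**Inputs not in the documents, assumed.** N = 12 or 20. k = period change divided by the within-order SD of the paired difference, from 0 to 1. No carryover. True effect set so that the paired t-test has 80% power at k = 0: 0.889 SD (N = 12) and 0.660 SD (N = 20). The SAP states no power calculation, so there is no figure of its own to reproduce.

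**Model.** Let D = intervention minus control, with SD 1 within order.

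- Harness first (n1 children): E(D) = effect − k
- Control first (n2 children): E(D) = effect + k
- Paired estimate: effect + k(n2 − n1)/N
- With equal orders, the SD of D is inflated by √(1 + k²N/(N−1)), roughly √(1 + k²). At N = 12 this is 1.03, 1.13 and 1.45 for k = 0.25, 0.5 and 1.
- Adjusted estimate: the mean of the two order-specific means, with SE ½√(1/n1 + 1/n2) and N − 2 df. It does not depend on k.

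**1. Equal orders.** The estimate is unbiased. Power (paired by simulation, adjusted from the noncentral t):

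| Split | k = 0.25 | k = 0.5 | k = 1 | Adjusted, any k |
|---|---|---|---|---|
| 6:6 | 78% | 72% | 48% | 79% |
| 10:10 | 78% | 72% | 49% | 80% |

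The adjusted figure at 6:6 uses SE = ½√(1/6 + 1/6) = 0.289 and noncentrality 0.889/0.289 = 3.08 on 10 df.

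**2. Unequal orders, given the split (harness-first:control-first).** At 4:8 the shift is k(8 − 4)/12 = 0.33k.

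- 4:8: the mean estimate is 0.889 + 0.167 = 1.06 (k = 0.5) and 0.889 + 0.333 = 1.22 (k = 1), about 19% and 37.5% too high.
- 8:4: it is 0.72 and 0.56, too low by the same amounts. Paired power is 54% and 17%, against 74% adjusted.
- 7:13 or 13:7: the shift is 0.30k, or 0.15/0.660 = 23% and 0.30/0.660 = 45% too high or too low.

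The type I error of the paired test at k = 1, given the split, is 0.6% at 6:6, 5.1% at 4:8, 15% at 3:9, 7.5% at 7:13 and 16.5% at 6:14. The adjusted test stays at about 5%.

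The protocol states no ratio or blocking. If randomisation were simple, the chance of a split at least this uneven is 39% for 4:8 and 15% for 3:9 (N = 12), and 26% for 7:13 and 12% for 6:14 (N = 20).

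**3. Averaged over simple randomisation.** Both estimates are unbiased and type I error is about 5%. Paired power is 80%, 78%, 71% and 50% at k = 0, 0.25, 0.5 and 1, for both N. Adjusted power is 75% (N = 12) and 78% (N = 20). The paired test is therefore ahead at small k and clearly behind at large k.

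**4. The fallback as named.** The rank-sum test is for independent groups. Applied to the two sets of condition scores it also discards the pairing. With normal data, N = 12, 6:6 and no period change, its power is 52% at a within-child correlation of 0.5 and 13% at 0.8. A rank-sum test of period differences between orders has 73%. How much is lost with non-normal data depends on the shape of the distribution, so no figure is given for that case.

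**The case against.** The strongest reply is that every size above rests on assumed inputs. N, allocation method and period change are all unstated, and a change of a full SD is not supported by anything in the documents. At k = 0.25 with equal orders the loss is about one point. The shift needs unequal orders. With balanced allocation and no differential dropout there is none, and the paired test errs on the conservative side. All of this stands, and it limits the severity.

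Adjustment also has a price. With no period change its power, against 80% paired, is 79% at 6:6, 74% at 4:8 and 67% at 3:9. Averaged over simple randomisation it loses until k reaches about 0.25 (N = 20) or 0.35 (N = 12, interpolated). At splits with more control-first children the paired test can even reject more often (87% against 74% at 4:8, k = 0.5), but only because its estimate is pushed upward.

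The figures assume no carryover, which is doubtful for GMFM. If period-1 gains persisted fully, control-first children would show D = harness gain and harness-first children D = −control gain. The adjusted estimate would then be half the difference in gains. Half of 0.889 at 6:6 gives about 29% power. The paired estimate is halved too at equal orders, so this limits what the fix achieves without favouring the present plan.

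The rank-sum wording may be a slip for signed-rank. That test keeps the pairing but still ignores period. With normal data at 6:6 its power is 76%, 73%, 67% and 40% at k = 0, 0.25, 0.5 and 1, against 73-74% for the replacement.

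Finally, this is an exploratory pilot with no power target. The SAP nevertheless tests every outcome at 0.05, and the replacement needs no extra data.

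**Conclusion.** The concern holds. The SAP's only between-condition tests ignore period in a design where the documents themselves make a period change plausible for Aims 1 and 2. The main consequence is lost precision: negligible at k = 0.25, about 7 points of power at k = 0.5 and about 31 at k = 1 with equal orders (79% against 72% and 48% at N = 12). If the orders end up unequal, the estimate from that split also moves by the period change times (control-first minus harness-first)/N, in a direction not known in advance. At very uneven splits with a large period change, false positives also rise. Averaged over randomisation the paired t-test remains valid and unbiased.

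These sizes rest on assumed N, split and k, which may differ by outcome, and on no carryover. This should be fixed, but it does not invalidate the trial.

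**What to change.** For each child compute d = period 1 minus period 2 on matching measurements. Compare d between the two randomised orders with a two-sample t-test, and report half the difference in means (harness-first minus control-first) with its 95% CI. A mixed model with treatment, period and sequence as fixed effects and child as a random effect is an alternative. For the fallback, apply the Wilcoxon rank-sum test to d between orders, and check normality of d within order.

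Pre-specify the matching pairs:

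- GMFM D and E: week 5 with week 9.
- DMQ-18: the same, with its timing stated.
- Coded behaviour: last session of week 4 with last of week 8, or first of week 2 with first of week 6.
- Activity counts: the same set of sessions from weeks 2-4 and weeks 6-8.

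Report the number of children per order, and state that the adjustment does not remove carryover, so for GMFM it is a partial remedy.

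The change is to SAP wording only. It needs no new data and can be run in SPSS. The statistical price is one degree of freedom, plus the power loss described above when orders are unequal and the period change is small. At 6:6 adjustment is behind only if k is below about 0.17.

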**Up and Down: Use of Dynamic Partial Body Weight Support
Play Environment to Encourage Upright Mobility and
Exploration in Infants with Down Syndrome (DS)**

NCT number:

Date:1/06/2022

Research objective

Children with Down syndrome (DS) experience delayed mobility, which decreases their opportunity for exploration and impacts the development of their cognitive, communication, and social-emotional skills. Physical therapy interventions for infants with DS frequently focus on the development of postural control and body weight support to enhance the development of motor skills. Partial body weight supported (PWBS) intervention, where part of the child's body weight is offloaded through the use of a harness and allows for easier movement through space, is an effective intervention for infants with DS, leading to earlier onset of independent mobility and increased physical activity. We are combining PWBS support for infants with DS who are not yet walking, within an enriched play environment to better understand how PWBS may impact their mobility, exploration, and overall activity level.

Research Design

This is a randomized, crossover pilot study design with the sampled children serving as their own controls

Methods

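### GMFM D and E: with equal orders, a harness gain still present at week 9 would shrink the planned post-test contrast, and no carryover-free check is planned

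*SAP*

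**What the plan says.** The Protocol (Research Design) describes a "randomized, crossover pilot study design with the sampled children serving as their own controls". Methods sets two three-week play periods, weeks 2-4 and 6-8, "with a washout and reassessment period during week 5 prior to crossover". It then adds: "A final reassessment session will be done during week 9".

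Aim 2 is worded "Explore the effects of a harness-based intervention on gross motor skill acquisition among infants with DS". Under that aim GMFM sections D and E are measured three times, at the first session (week 1 under Methods), in week 5 and in week 9. The week 5 visit is therefore the post-test of the first period, and it falls in the washout week.

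The SAP (Data Analysis) makes the raw D and E scores dependent variables and plans paired t-tests "comparing the control post-tests to the intervention post-tests". The non-normal fallback changes the test but names no other scores to compare. The only other output is general: "Descriptive statistics will be reported for each variable". Neither document plans a comparison of the orders at week 5, an adjustment for the week 1 score, or a table by order and visit.

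**The concern.** A washout removes effects that wear off. Aim 2 is about acquiring motor skills, and a skill, once acquired, may stay. In harness-first children the control post-test is the last visit, so any harness gain still held then counts towards control. With equal orders, the better the gain is kept, the smaller the planned estimate becomes.

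This matters because a pilot informs later work. A planner who sees a small GMFM difference could not tell from the planned output whether the effect was small or had been retained. Persistence is plausible but not shown, since the documents give no retention figure.

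**Working it through.** The plan states no effect size, SD, sample size or power for GMFM, so there is no figure to reproduce.

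**Inputs.** The visit times and the contrast come from the documents. The following are assumed symbols:
- T: harness gain over unharnessed play at the end of the harness period.
- r: share of T still present at week 9 in harness-first children, between 0 and 1.
- g1, g2: growth from week 1 to 5 and from week 5 to 9, common to both orders.
- p: share of children who are harness-first.
- b: starting score.

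**Expected scores.**

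| Order | Week 1 | Week 5 | Week 9 |
|---|---|---|---|
| Harness-first | b | b + g1 + T | b + g1 + g2 + rT |
| Control-first | b | b + g1 | b + g1 + g2 + T |

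**Planned contrast (intervention minus control post-test).**
- Harness-first: week 5 minus week 9 = T(1 - r) - g2.
- Control-first: week 9 minus week 5 = T + g2.
- Mean over children: T(1 - pr) + g2(1 - 2p).

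**Equal orders (p = 1/2).** Growth cancels and the mean is T(1 - r/2). At r = 0, 0.5 and 1 this is 1.00T, 0.75T and 0.50T. Simulated means with T = 3 and N = 12 were 3.00, 2.25 and 1.50.

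**Unequal orders.** Take T = 3 and g2 = 2.
- p = 1/3: 3(1 - r/3) + 2/3 = 3.67, 3.17 and 2.67, or 122%, 106% and 89% of T at r = 0, 0.5 and 1.
- p = 2/3: 3(1 - 2r/3) - 2/3 = 2.33, 1.33 and 0.33, or 78%, 44% and 11%.

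**Which interval matters.** The bias enters only through the harness-first week 9 score. A gain still present in week 5 but gone by week 9 has r = 0 and causes no bias.

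**First-period comparison.** Week 5, harness-first minus control-first: (b + g1 + T) - (b + g1) = T, whatever r is. No child has crossed over, so carryover cannot enter.

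**Precision of that comparison.** Simulation, 20,000 trials per setting, with ANCOVA adjusted for week 1. Assumed N = 12 in equal orders, T = 3, growth 2 per period (SD 0.3), error SD 1 and between-child SD 5, unless varied.
- Mean 95% interval half-width: 1.9 in the base setting, 2.3 at growth SD 1, 3.3 at growth SD 2, 3.7 at error SD 2.
- Root mean squared error, planned v ANCOVA, at r = 0 / 0.5 / 1: base 0.42 v 0.88 / 0.86 v 0.88 / 1.56 v 0.88; error SD 2: 0.82 v 1.67 / 1.12 v 1.70 / 1.72 v 1.66.

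**What a table by order and visit can show.** The harness-first change from week 5 to 9 is g2 - T(1 - r). The control-first change from week 1 to 5 is g1. The gap is (g2 - g1) - T(1 - r), which reflects retention only if g1 = g2. With T = 3, g1 = 2 and r = 0.5:
- g2 = 2: 0 - 1.5 = -1.5, the correct reading.
- g2 = 3.5: 1.5 - 1.5 = 0, which looks like full retention.
- g2 = 0.5: -1.5 - 1.5 = -3, which looks like none.

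**The case against.** The strongest reply is that the size is wholly assumed, in a pilot whose aims are all exploratory. T is the harness increment over play in the same enriched setting, and nothing shows that it lasts while harness-first children go on playing there without the harness. The proposed check is also weak. At an assumed N of 12, half-widths of 1.9 to 3.7 around an effect of 3 will often fail to separate a small effect from a retained one. In the noisier setting the planned contrast has the lower error at r = 0 and 0.5 and is about equal at r = 1. All of this stands. It is why the severity is low and the planned contrast keeps the lead. It does not remove the gap: no planned analysis is free of the dependence on r.

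A reader might infer three stronger things that the documents do not support:
- *Any gain that outlasts the one-week washout biases the result.* It must still be present at week 9, after three further weeks of control play.
- *The trial will understate the effect.* The documents give neither r nor the balance of the orders, and with fewer harness-first children the net error can be upward.
- *A table by order and visit would reveal retention.* It would do so only under equal growth in both periods. Eligible children are "under 36 months of age, able to sit independently" but not yet walking, and their rates of change may well differ between periods. A larger sample would not cure this.

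**Conclusion.** The point holds as a low-severity gap. For GMFM D and E the only planned comparison estimates effect x (1 - r/2) with equal orders, so it loses up to half the effect if the whole gain is kept to week 9 and nothing if none is. With unequal orders the error depends on growth as well, and its direction is not fixed. These results rest on growth common to both orders, r between 0 and 1, and a linear model that ignores possible floor scores in children who do not yet walk. That the plan contains no carryover-free check follows from the documents alone. The point does not show that the planned contrast is the wrong lead analysis.

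**What to change.** Keep the planned post-test contrast as the lead. For GMFM D and E only, add to the SAP:

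1. One pre-specified sensitivity analysis: the week 5 score compared between randomised orders by ANCOVA, adjusted for the week 1 score. Report it as an estimate with a 95% confidence interval and no added significance claim.
2. Means and SDs by order and visit (weeks 1, 5 and 9), labelled as description. State that setting the harness-first change from week 5 to 9 against the control-first change from week 1 to 5 reflects retention only if growth is equal in both periods. State also that it will not be used to choose which analysis to report.

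A contrast of changes within each period should not serve as the check. In the same model with equal orders it estimates T(3 - r)/2, which is 150%, 125% and 100% of the effect at r = 0, 0.5 and 1.

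The cost is a few lines of SAP text, one model and one table, with no new data. The downside is precision: the ANCOVA compares children with each other, so its interval will be wide in a small pilot.

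### The non-parametric fallback is an independent-samples test (Wilcoxon Rank Sum), although the crossover data are paired

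*SAP*

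**What the plan says.** The Protocol (Research Design) describes a "randomized, crossover pilot study design with the sampled children serving as their own controls", and the Methods section repeats this. Every child is observed under both conditions, in weeks 2-4 and weeks 6-8, "with a washout and reassessment period during week 5 prior to crossover".

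In the SAP (Statistical Design and Power, Data Analysis), the main test respects that structure: "paired t-tests will be performed comparing the control post-tests to the intervention post-tests". Two further sentences set the fallback. The trigger is "Prior to statistical analysis, we will test the data for normality", and the consequence is "If the data is not normally distributed, differences will be determined using the Wilcoxon Rank Sum test".

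The rule applies to every dependent variable listed there: "exploratory behavior activity counts, exploratory behavior coding counts, GMFM sections D and E raw scores, and DMQ-18 raw scores". Alpha is 0.05, with no statement of one- or two-sided testing.

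**The concern.** A skewed distribution is a reason to move from a t-test to a rank test. It is not a reason to move from a paired to an unpaired comparison, because the design has not changed. The fallback as named treats a child's two values as if they came from two unrelated children.

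The trigger is also loose. The SAP does not say whether normality is checked on the raw scores or on the within-child differences, and the paired t-test depends on the differences. Skewed raw scores could therefore send an outcome to the unpaired test even when its differences are well behaved.

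With positive within-child correlation, the stake is a missed effect rather than a false positive. With negative correlation the direction reverses.

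**Working it through.** **Inputs.** From the documents: paired crossover data, paired t-test as main analysis, Rank Sum as fallback, alpha 0.05. The documents give no number of children (n), effect size, SD or within-child correlation (rho), so there is no planned figure to reproduce. Assumed for illustration: two-sided testing, equal SDs, n = 12 and 20, rho from -0.3 to 0.7, a fixed shift of 0.5 or 1 between-child SD (on the log scale for lognormal data), and no period effect.

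**Check by formula (large sample, means).** The true variance of the mean difference is 2(1 - rho)/n in SD units. A test that ignores pairing uses 2/n. Its actual two-sided size is therefore 2 x [1 - Phi(1.96 / sqrt(1 - rho))]:

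- rho -0.3: 8.6%
- rho 0: 5.0%
- rho 0.3: 1.9%
- rho 0.5: 0.56%
- rho 0.7: 0.03%

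For power at n = 20, shift 0.5 SD, rho 0.5, the standardised shift is 0.5 x sqrt(20/2) = 1.581.

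- Pairing ignored: Phi[(1.581 - 1.96)/0.707] = Phi(-0.536) = 30%.
- Pairing used: Phi[1.581/0.707 - 1.96] = Phi(0.276) = 61%.

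**Check by simulation of the rank tests themselves** (20,000 trials per setting, Monte Carlo error under 1 point). Type I error of Rank Sum, over n = 12 and 20 and both normal and lognormal data:

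| rho | Rank Sum |
|---|---|
| -0.3 | 7.6% to 8.4% |
| 0 | 4.5% to 4.9% |
| 0.3 | about 2% |
| 0.5 | about 0.9% |
| 0.7 | 0.2% |

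Signed-rank stayed between 4.1% and 4.9%.

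Power, Rank Sum vs signed-rank:

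| Data | n, shift | rho 0.3 | rho 0.5 | rho 0.7 |
|---|---|---|---|---|
| Normal | 12, 1 SD | 63% vs 72% | 65% vs 85% | 69% vs 97% |
| Normal | 20, 0.5 SD | 29% vs 41% | 27% vs 55% | 24% vs 76% |
| Normal | 20, 1 SD | 89% vs 94% | 92% vs 98% | 95% vs 100% |
| Lognormal | 12, 1 SD | 63% vs 66% | 65% vs 79% | 69% vs 94% |
| Lognormal | 20, 0.5 SD | 29% vs 37% | 27% vs 48% | 23% vs 68% |
| Lognormal | 20, 1 SD | 89% vs 90% | 92% vs 96% | 95% vs 100% |

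The gap runs from about 1 point (89% vs 90%) to about 52 points (24% vs 76%). At rho 0 nothing is lost (normal, n = 12, 1 SD: 61% vs 57%).

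**Very small n.** The smallest attainable exact two-sided p is 2/2^n for signed-rank: 0.0625 at n = 5 and 0.031 at n = 6. For Rank Sum it is 2/C(2n, n), which is 2/70 = 0.029 at n = 4. With five or fewer non-zero pairs, exact signed-rank cannot reach 0.05. At n = 6, rho 0.3 and a 0.8 SD shift (normal data), the two tests have about equal power (both near 18%).

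**The case against.** **It is probably one wrong word.** The fallback follows directly on a comparison the SAP has just called paired, and nothing suggests an intention to unpair. That is likely. But the SAP is what the analyst follows: a literal reading runs the wrong test, and a silent substitution departs from the plan.

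**Rank Sum has a legitimate crossover use.** It can compare within-child period differences between the two sequence groups. True, but the SAP mentions neither sequence groups nor period differences, so this reading does not rescue the text. If it was intended, it has to be written down.

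**The power figures assume no period effect.** This stands. Infants followed over nine weeks may well develop between periods, although the size of any such effect is an assumption. With balanced sequences, normal data, n = 20, rho 0.5 and a 0.5 SD shift, power for Rank Sum vs signed-rank is 27% vs 54% with no period effect, 24% vs 44% with a 0.5 SD period effect, and about 17% vs 22% with a 1 SD period effect. The type I error of signed-rank also falls, to 2.7% and 0.5% for those two period effects. The tabulated gains are therefore towards the upper end, but signed-rank remains valid and is no worse than Rank Sum in these settings.

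**It carries little weight in a pilot.** The aims are exploratory, the error is conservative under positive correlation, and nobody can say how often the fallback would be used. This holds the severity down. It does not make the rule right.

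**Conclusion.** The fallback is wrong as written: it names an independent-samples test for paired data, and no passage supplies the paired alternative or a sequence-based use of Rank Sum. That conclusion rests on the text alone.

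The consequence is conditional. With positive within-child correlation, Rank Sum is conservative and, from about a dozen children upward, gives up power by an amount that depends jointly on n, effect size, correlation and any period effect, so no single figure holds. With zero correlation nothing material is lost, and with negative correlation the test is anti-conservative (about 8% at rho -0.3). At six or fewer children the power advantage of signed-rank can shrink, vanish or reverse.

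The point should be fixed before analysis, at the low end of that category, given the exploratory purpose and the unknown use of the fallback.

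**What to change.** In the SAP's Data Analysis section, replace the Wilcoxon Rank Sum test with the Wilcoxon signed-rank test on the within-child differences (intervention minus control), and state that normality is assessed on those differences. If a Rank Sum comparison of period differences between sequence groups was meant, describe that analysis explicitly instead.

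Optionally, add that an outcome with five or fewer non-zero pairs is reported descriptively, because the exact two-sided signed-rank test cannot then reach 0.05.

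The cost is one or two sentences, with no change to data collection, visits or design.
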